### Safety of EC products.

Our current ECIG study suggests

**Table 4.** Recommended Adverse Event Recording Guidelines.

Attribution	Grade 1	Grade 2	Grade 3	Grade 4	Grade 5
Unrelated	Phase I	Phase I	Phase I Phase II	Phase I Phase II Phase III	Phase I Phase II Phase III
Unlikely	Phase I	Phase I	Phase I Phase II	Phase I Phase II Phase III	Phase I Phase II Phase III
Possible	Phase I Phase II	Phase I Phase II Phase III			
Probable	Phase I Phase II	Phase I Phase II Phase III			
Definitive	Phase I Phase II	Phase I Phase II Phase III			

that will (1) directly compare longer-term use of the NIDA SRECs to commercial EC devices among EC-naïve and experienced male and female dual users, and (2) compare the SREC to EC devices with higher nicotine yields, such 36 mg/ml, a dose that we are using in a current funded study (2015-0638), among male and female adult CC smokers.

## E. PROTECTION OF HUMAN SUBJECTS

### Risks to the Subjects

#### ***Human Subjects Involvement, Characteristics, and Design***

The Houston population is estimated at over 4 million with an ethnic distribution of 59% Caucasian, 19% African-American, 5% Asian, and 0.4% Native American, with 33% Hispanic or Latino of any race . We expect to recruit English-speaking minority smokers in proportion to the population demographics, and smoking prevalence. Inclusion and exclusion criteria are listed in **Table 1**. All smokers meeting these qualifications will be accepted into the study. All data collection will occur at MD Anderson Cancer Center.

#### ***Study Procedures, Materials, and Potential Risks***

Participants will be providing biological samples in the form of urine (nicotine, cotinine, anabasine, nicotelline), and vitals. Questionnaire data will be obtained that assess previous smoking, smoking cessation history, current and past health and psychiatric conditions, mood, CC dependence, EC dependence, nicotine withdrawal, craving, and cigarettes smoked. All data will be collected specifically for research purposes and will be assigned a subject identification number in the Tobacco Research and Treatment Program (TRTP) database and an accession number in CORe to maintain confidentiality. The official database for this study is the TRTP database (APPID-264846) maintained by in-house data programmers. Relevant medical screening data will be shared with the participant as appropriate for referral and follow-up medical care. It is highly unlikely that any legal, social, or psychological problems will result from this research. Any participant who spontaneously reports mood, hopelessness, anxiety and/or other symptoms suggesting a persistent change in mood, or who expresses suicidality, will activate the mental health procedures described in Appendix T. Any individual who is deemed ineligible for study participation for medical/psychiatric reasons will be referred to local medical and/or psychiatric resources.

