**Exclusion Criteria:**

- Individuals who report depressive symptoms in the moderately severe or severe range on the PHQ-9 (scores of 15 or above) or who report current suicidal ideation on the PHQ-9
- Uncontrolled or unstable medical condition (e.g., uncontrolled hypertension, angina, diabetes).
- Evidence of cognitive deficits or instability that would preclude reliable study participation.
- Being pregnant, engaging in breast-feeding, or being of childbearing potential and engaging in sexual activity that could lead to pregnancy and is not protected by a medically acceptable, effective method of birth control while enrolled in the study, as determined by self-report. Medically acceptable contraceptives include: (1) approved hormonal contraceptives (such as birth control pills, patches, implants or injections), (2) barrier methods (such as a condom or diaphragm) used with a spermicide, or (3) an intrauterine device (IUD). Contraceptive measures sold for emergency use after unprotected sex are not acceptable methods for routine use.
- Considered by the investigator to be an unsuitable or unstable candidate (including but not limited to the following situation: unwilling or unable to comply with study procedures)
- Individuals who reside in an area that is outside of our shipping company's area of operation or in a jurisdiction outside of our medical staff's licensure (if unable to attend in-person clinic visits) AND who decline or are unable to come in to clinic to provide necessary samples and/or collect study products.

or virtual visit (up to \$100) (excluding the telephone AE follow-up), up to \$40 for completing

To facilitate participant retention and compliance with study procedures, we will offer financial compensation. Enrolled participants will have the opportunity to receive a potential maximum compensation of \$522 each (see Appendix V). Participants will be compensated up to \$25 for each in-person

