Participants will be instructed to smoke *ad libitum* prior to this session. Prior to the session, the participant will be asked to complete basic demographics, smoking, tobacco product use, and health history questionnaires used in our previous studies  that will be reviewed and approved for eligibility by a licensed medical provider following the visit. CC, SREC, and other tobacco product use eligibility criteria will be evaluated using a timeline follow back procedure  and smoking history measures used in previous studies . These questionnaires may be pushed by our institutional Qualtrics server to be completed electronically (via text or email) prior to the session. Current major depressive disorder (MDD) and suicidality will be identified using the Patient Health Questionnaire (PHQ-9; see Appendix L) . The screening session and the three return visits are each expected to last approximately 3 hours. The final safety telephone call will assess any ongoing adverse effects and should last approximately 10 minutes.

**COVID-19 adaptation:** Eligible participants will be scheduled for a virtual screening session using an institutionally approved platform, such as Zoom. If we are unable to collect any required biological specimens through mail, the participant may be asked to go in-person to conduct the tests through an approved collection site. Approved sites may include University of Texas MD Anderson, University of Texas sister institutions including the Center for Neurobehavioral Research on Addiction (CNRA) at University of Texas Medical School, other universities or hospitals located in Texas, and/or contracted commercial vendors.

**Baseline Medical Clearance.** Following the completion of the baseline visit, a member of the medical team (Physician assistant and/or the Physician) will review all relevant data collected at screening and will provide their clearance for the participant to proceed to Visit 1. The study Physician will have the final review of the data and will complete the final eligibility sign off prior to randomization. In the event the Physician is not able to sign-off prior to the visit (due to being out of office), the Principal Investigator may provide the initial sign-off so that the visit may proceed, and the physician will sign-off upon their return.

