**Adverse Event Safety Assessment.** 30 days (+/- 7 days) following the end of Phase 3, study participants will complete a telephone visit with study staff to assess ongoing adverse events.

**Post-study smoking cessation treatment.** We will offer all participants 8 weeks of free smoking cessation treatment, which may include nicotine replacement therapy (NRT; nicotine patch and lozenge) and smoking cessation counseling, at the end of their study participation. Alternatively they may be referred to another smoking cessation study. It is not the intention of this phase of study to evaluate the efficacy of EC for smoking cessation, but rather to facilitate smoking cessation by offering free treatment at the conclusion of EC exposure. This fulfills what we see as a strong ethical obligation to treat smokers that enter our research programs. NRT and counseling will be administered by MD Anderson's Tobacco Treatment Program (TTP), headed by Drs. [name] (Co-I) and [name] (Co-I), which provides free treatment to all

**Table 2.** Project measurement, by time point.

Week	-1	0	2	4	6	10
Visit	T0	0	1	2	3	T1
Telephone contact	x					x
In-person or virtual Session		x	x	x	x	
Initial baseline measures:						
Initial eligibility screen (e.g., age, nicotine product use)	x					
Demographics, smoking, tobacco product use, and health history		x				
PHQ-9	x					
Tobacco Products and Risk Perceptions Survey (TPRPS)	x					
Environmental Tobacco Smoke Exposure Questionnaire (ETSEQ)	x					
Product Use:						
Timeline Follow Back (TLFB) of CC & other product use	x	x	x	x	x	
Timeline Follow Back (TLFB) of SREC use			x	x		
Urine sample to measure nicotine, cotinine, nicotelline and anabasine		x	x	x		
Smartphone EMA of product use 	x	x	x	x		
Ongoing Adverse Event (AE) Assessment			x	x	x	
Health Changes Questionnaire		x	x	x		
Product Acceptability:						
Product Evaluation Scale (PES) - CC	x	x	x	x		
Product Evaluation Scale (PES) - SREC			x	x		
Perceived Health Risk Questionnaire (PHRQ) – CCs & ECs	x	x	x	x		
Perceived Health Risk Questionnaire (PHRQ) – SRECs			x	x		
Implicit Association Test (IAT) – CCs & ECs	x	x	x	x		
Brief Smoking Consequences Questionnaire-Adult (BSCQ-A)	x	x	x	x		
EC-specific Brief Smoking Consequences Questionnaire-Adult (EC-BSCQ-A)	x	x	x	x		
Product Reinforcement:						
Purchase task (PT) - CCs	x	x	x	x		
Purchase task (PT) - SRECs			x	x		
Respiratory Health and Symptoms						

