**Assessment of nicotine dependence symptoms.** As part of Aims 1 & 2, participants will complete questionnaires assessing nicotine dependence symptoms, including CC dependence (Fagerström Test for Cigarette Dependence [FTCD; formerly the FTND; see Appendix C]), EC dependence (Penn State Electronic Cigarette Dependence Index [PSECDI; see Appendix J]), nicotine withdrawal (Minnesota Nicotine Withdrawal Scale-Revised [MNWS; see Appendix H]), affect (Positive and Negative Affect Scales [PANAS; see Appendix I]), and craving to smoke (Questionnaire of Smoking Urges-Brief [QSU-Brief; see Appendix N]) at each study visit.

During all phases, SMS/Qualtrics will be used to collect 2 daily random smartphone EMA measures of nicotine dependence symptoms, including nicotine withdrawal, craving, and affect, based on 8 items from the QSU, PANAS, and MNWS. Further details about the 2 daily smartphone EMA measures, as well as the once daily assessments of product use, are described above in the "Assessment of product use" section.

**Assessment of respiratory and other symptoms.** We will also assess respiratory symptoms at each visit using the American Thoracic Society questionnaire (ATSQ). The ATSQ is an 8-item questionnaire that assesses symptoms including coughing, wheezing, phlegm production, shortness of breath. An email will be sent to project staff when a participant completes the ATSQ and has a total score of >3 on questions #4-8. Staff will assess symptoms with the participant at the next visit. If symptoms present prior to the start of study product (V0 or V1), staff will add the conditions to the medical history. If the elevated score presents while on study product, staff will assess changes in symptoms and severity and log an adverse event, if indicated.

Study Medical Monitor [name] will oversee the collection, review, and attribution of adverse events (AEs) in this study and will consult with [name] on respiratory-

related AEs, as needed. The physician may delegate to other members of the medical team the task of a preliminary review of the adverse event, attribution, and recommended action plan. The physician will then complete the final review of the adverse event, confirm attribution and sign off on the adverse events.

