that use of a closed-tank ECIG device among adult smokers results in relatively few adverse events. In this protocol (2015-0638; R01DA042526), which is ongoing, we are testing the strategy of simultaneously providing a smoker uninterested in quitting with both VLNCs as well as an ENDS product to determine if they will compensate for the reduction in nicotine from the VLNC's with the ENDS product. This is critical to the regulatory strategy aimed at determining nicotine levels in future ENDS product, because we may wish to maximize compensation in order to move people away from combustibles and increase the likelihood of cessation. Thus far, we have exposed 176 adult smokers to NIDA's VLNC combustible cigarette for up to 9 weeks and to commercially available closed-tank electronic cigarettes for up to 6 weeks (the same product being used in many other studies across the country). In terms of adverse events, similar proportions of participants have reported adverse events during the exclusive cigarette phases (18.0%) than during the phase where they are encouraged to use electronic cigarettes instead of smoking (15.3%). The most frequently reported adverse events during the electronic cigarette phases included depressive symptoms (n=4), sore throat (n=3), diarrhea (n=2), toothache (n=2), and vomiting (n=2). For the exclusive cigarettes phases, the most common adverse events included cough (n=6), irritability (n=5), headache (n=4), back pain (n=2), diarrhea (n=2), limb edema (n=2), insect bite (n=2), nausea (n=2), panic attack (n=2), and urinary tract infection (n=2). No severe adverse event was reported during the electronic cigarette phases, but one was reported during the exclusive cigarette phases, brachycardia (n=1). None of these were determined to be of probable or definitive relation to the study product. No serious respiratory symptoms have been reported. Our retention rate through the end of study has been 77%. The preliminary findings suggest that closed-tank electronic cigarettes are not associated with more adverse events than smoking combustible cigarettes.

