**Adverse experiences associated with specimen collection.** The collection of urine by the participants using specimen cups are not expected to result in adverse events.

**Adverse experiences associated with electronic cigarettes.** Use of ECs has been found to increase the risk of acute upper respiratory irritation, cough, phlegm production, headache, dry mouth/throat, vertigo, and nausea . Participants using SRECs, particularly the placebo version, may experience nicotine withdrawal effects, including increased irritability, difficulty concentrating, insomnia, anxiety, dysphoria, and hunger. None of these effects should result in serious adverse health consequences. However, it is possible that e-cigarettes may cause lung injuries or other serious health problems, which study medical monitor [name] and his team will monitor, along with our collaborator from the Department of Pulmonary Medicine, [name].

In the event of a new health risk associated with the electronic cigarettes used in this protocol that is identified, we will take the following steps: (1) the newly identified risk will be discussed within 5 days by study chair [name], collaborator and Study Physician [name], pulmonology collaborator [name], and collaborator [name] to determine its relevance to the study products used in this protocol; (2) if the risk is deemed by the collaborators to be related to the study products used in this protocol, we will contact all active subjects by phone within 5 days and submit a PI memo to MD Anderson's IRB and IND offices that describes this new health risk (also within 5 days); (3) Upon determination by the IRB, the protocol and ICD will be revised to incorporate information about the newly identified risk, the DSMB will be informed at the next semi-annual review of this protocol, and active participants will be reconsented with the details of these new risks. We will keep a log of any new risks communicated by the CDC and/or the Texas HHS that are deemed relevant to the study products used in this protocol, including participants who are contacted and/or reconsented and the date of this contact.

**Adverse experiences associated with questionnaires.** It is unlikely that completing questionnaires would lead to any potential risks for participants, although some participants may

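### On product, depression and suicidality are detected only by participant report or adverse event assessment; the PHQ-9 is not repeated and no mood score has a stated trigger

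*Combined protocol and SAP*

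**What the plan says.** **At entry.** Under Procedures, the screening session (V0) states that "Current major depressive disorder (MDD) and suicidality will be identified using the Patient Health Questionnaire" (PHQ-9). Table 1 excludes people who score 15 or above or who report current suicidal ideation. Table 2 gives the PHQ-9 a single mark, in the block of initial baseline measures.

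**On product.** Under Measures, the PANAS and MNWS are completed at each visit. Two random smartphone prompts a day cover "nicotine withdrawal, craving, and affect, based on 8 items from the QSU, PANAS, and MNWS". Table 2 also lists a "Health Changes Questionnaire", whose items are not shown. Specific Instructions for Adverse Events Recording places adverse event recording at V2 and V3; the later 30-day call covers ongoing events only.

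**Expected effect.** Adverse Events and Serious Adverse Events warns: "Participants using SRECs, particularly the placebo version, may experience nicotine withdrawal effects, including increased irritability, difficulty concentrating, insomnia, anxiety, dysphoria, and hunger". It adds that none of these should have serious health consequences.

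**Stated response.** Study Procedures, Materials, and Potential Risks provides that "Any participant who spontaneously reports mood, hopelessness, anxiety and/or other symptoms suggesting a persistent change in mood, or who expresses suicidality" activates Appendix T. Adverse Events and Serious Adverse Events adds that reports of suicidal ideation, depression or anxiety thought to be treatment-related lead, where possible, to psychological assessment, with management set by the addiction psychiatrist.

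**Comparator.** For respiratory symptoms the plan goes further. "An email will be sent to project staff when a participant completes the ATSQ" and scores above 3 in total on questions 4 to 8, and staff then assess the symptoms at the next visit.

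**The concern.** The protocol predicts low mood and anxiety during SREC use, most of all on placebo, and every participant who completes both phases receives placebo. Depressive symptoms also head the list of e-cigarette-phase adverse events in Safety of EC products. Yet the one instrument chosen to find depression and suicidality is used only to decide entry. Product starts after the two-week usual-brand phase, so that screen is at least two weeks old at first SREC use and about six weeks old at V3.

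Mood data do arrive during SREC use, but nothing visible in the protocol turns a bad score into a call to staff. A participant whose mood worsens markedly, or who develops suicidal thoughts without mentioning them, could pass through a product phase unnoticed unless the matter surfaces at an adverse event assessment. What is at stake is the safety of individual participants, not the estimate of the effect on cigarettes per day.

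**Working it through.** The plan states no figure to reproduce. The check is a count of assessments and triggers, followed by the scale of the problem and the workload of the fix.

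**1. Assessments and triggers** (Table 2, Table 1, Measures)

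| Measure | Before product | On product | Stated score that prompts action |
|---|---|---|---|
| PHQ-9 | once | none | 15 or above, or current suicidal ideation: entry exclusion only |
| PANAS, MNWS | weeks 0, 2 | weeks 4, 6 | none |
| Smartphone affect items | 2 a day, weeks 1-2 | 2 a day × 28 days = 56 prompts | none |
| ATSQ (respiratory) | weeks 0, 2 | weeks 4, 6 | above 3 on questions 4-8: email to staff |
| Adverse event assessment | not applicable | V2, V3 | not score-based |

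The columns of Table 2 appear shifted in the extracted text, so the PHQ-9 mark may belong to the telephone screen or to V0. Both precede product. Measures repeats only the instruments described in that section, and the PHQ-9 is described earlier, under Procedures. The count is one score-based alert for respiratory symptoms and none for mood on product. Report-based routes for mood or suicidality do exist: Appendix T, and the psychological assessment described with adverse events.

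**2. Do such events occur?** Safety of EC products reports 4 depressive-symptom events in the e-cigarette phases among 176 exposed smokers.

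- 4 / 176 = 2.3%, exact 95% CI 0.6% to 5.7%, assuming four different people and that all 176 entered those phases.
- If only the 77% retained did so, 0.77 × 176 ≈ 136 and 4 / 136 = 2.9%.
- Applied here at 2.3%: 164 participants (Power and Sample Size) give 3.7 people, and 196 (Participants) give 4.5. Across the interval: 0.62% × 164 = 1.0 to 5.72% × 196 = 11.2.

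These are events that adverse event recording did capture. They show that depressive symptoms occur in this kind of study. They do not estimate how many are missed, and the documents offer no figure for that.

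**3. Workload of repeating the PHQ-9**

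| | V2 and V3 | V1, V2 and V3 |
|---|---|---|
| Forms, 164 participants | 2 × 164 = 328 | 3 × 164 = 492 |
| Forms, 196 participants | 2 × 196 = 392 | 3 × 196 = 588 |
| At 75% attendance (Measures) | 246 or 294 | 369 or 441 |
| Positives, low end (1%) | 246 × 0.01 = 2.5 | 369 × 0.01 = 3.7 |
| Positives, high end (5%) | 392 × 0.05 = 19.6 | 588 × 0.05 = 29.4 |

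The 1% to 5% positive rate is an assumption; the documents give none. Table 3 puts first enrolment at month 6 and last follow-up at month 22, which is 16 months. The high ends are then 19.6 / 16 = 1.2 and 29.4 / 16 = 1.8 positives a month.

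**The case against.** The strongest reply is that the plan already covers mood well. Entry removes people with moderately severe symptoms or suicidal ideation. On product there are two mood-related questionnaires at each visit, up to 56 affect prompts, adverse event assessment at both phase ends, a medical monitor and six-monthly DSMB review. Protection against Risks describes a clinic team with an addiction psychiatrist and several clinical psychologists. Each phase lasts two weeks, and usual-brand smoking is not penalised. All of this stands, and it is why the gap is small. What it leaves out is a stated link from a score to those staff.

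A reader might infer that the plan has no response to suicidality on product, or that mood goes unmonitored there. The documents do not support either reading. Expressed suicidality activates Appendix T, and affect is measured throughout. A reader might also take the 4 of 176 as cases the plan would miss, or as caused by e-cigarettes. Neither follows. The events were recorded, and that study also supplied very-low-nicotine cigarettes. Its exclusive-cigarette phases had irritability (n=5) and panic attack (n=2), and overall event proportions were similar (15.3% in the e-cigarette phase, 18.0% in the cigarette-only phases). None was judged probably or definitely related. Preliminary Studies likewise reports no rise in depression in earlier very-low-nicotine cigarette work.

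A third objection is that a trigger may exist out of sight. Appendix T, the adverse event forms, the Health Changes Questionnaire and the Data and Safety Monitoring Plan section cited under Protection against Risks are not in the supplied text. This stands, and the fix allows for it.

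Finally, V2 and V3 fall at phase end, V3 comes after all product use, and same-day review is stricter than the ATSQ rule. It is true that only V2 can change later exposure, and that nothing is added within a phase. But order is counterbalanced, so V3 closes the placebo phase for half the participants. Without it they would have no PHQ-9 after the phase in which dysphoria is most expected. A positive at V3 can still lead to care. Same-day review is a judgement suited to suicidal ideation.

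**Conclusion.** The point holds in a limited form. In the visible protocol, depression or suicidality during SREC use comes to light only through participant report or the adverse event assessments at V2 and V3. The PHQ-9 is given once, before product, and no mood or suicidality score on product has a stated trigger, although the ATSQ shows that such an alert is within the study's means.

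The size is small: low severity, a modest expected risk, and no effect on the primary result. The number of cases that would otherwise be missed cannot be estimated from the documents. The conclusion assumes that the unseen appendices, forms and monitoring plan contain no score-based trigger. If one of them does, what remains is a missing cross-reference.

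**What to change.** Repeat the electronic PHQ-9 at V2 and V3, and optionally at V1 as a fresh check before first product. Have it completed during the visit. Recruitment and Retention Plan pays participants for completing questionnaires beforehand, so the form should be kept out of that batch. A score of 15 or more, or any suicidal ideation, should alert staff through Qualtrics for same-day review and start Appendix T. Make this a review trigger, not a stopping rule; what follows is for the medical team. State it in Study Procedures, Materials, and Potential Risks, add the marks to Table 2, and tabulate the scores by product. If one of the unseen documents already holds such a trigger, cite it in that section instead.

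The cost is one nine-item form at two or three existing visits, one added alert condition, and a few minutes per visit. The main new duty is same-day review of a small number of positives, including for participants seen virtually. The staff needed are already described under Protection against Risks.
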